### **Secondary Objectives**

1. Determine if the Relaxing Environment Package reduces a patient's pain during office administration of intra-detrusor onabotulinum toxin A injections based on a visual analog scale.
2. Determine if the Relaxing Environment Package increases patient satisfaction with their procedure experience based on a visual analog scale.
3. Determine if the Relaxing Environment Package decreases procedure staff burnout based on a visual analog scale.

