### **Sample Size**

Our sample size calculation was based on a prior study within the urogynecologic population which showed a statistically significant reduction in VAS-anxiety when aromatherapy was used during multichannel urodynamics, a common urogynecologic office procedure. With a sample size of  $n=80$  we would have 80% power to detect a mean clinically important difference of 12mm out of 100mm on the anxiety visual analog scale assuming a standard deviation of 18.8 and p-value 0.05. As the intervention is delivered at the week level, if we reach  $n=80$  early in the week, we will plan to finish out the week and thus may reach a total sample size slightly greater than 80, increasing statistical power.

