#### **Group 2:** Control

- Non-aromatic (placebo) sticker on patient, procedure staff, MD lapel
- No music playing
- Overhead lights on
- Stirrups used

In order to create the least disruption to our clinical workflow, we propose randomizing the weeks of the study rather than randomizing participants. Permuted block randomization will be used such that a random sequence of blocks of 4 or 6 weeks (totaling to the number of weeks planned for the study) will be chosen. Within each block of 4 or 6 weeks, the weeks will be equally randomized to treatment or control. For example, within a four-week block, two of four weeks will be randomized treatment and two to control. Permuted block randomization will ensure that (i) prognostic factors (e.g., first-time vs. repeat patient) are balanced over the course of the study and (ii) seasonality is addressed (e.g., within summer, half of the weeks are control and half treatment). Each week of the study will be randomized to either Relaxing Environment Package or Typical Office Environment (control), rather than randomizing individual patients. On Monday of every week, an envelope will be opened to determine if it is a Relaxing Environment Package week or Control week. Randomization will be discussed in more detail below.

If the week is randomized to a *Relaxing Environment Package*, the patient, procedure staff, and MD will enter the procedure room and receive a lavender aromatherapy sticker to be worn on their lapels. The lavender aromatherapy sticker will be ordered from Aroma Stickers store website (<https://aroma-stickers.com>). Calming music from Sirius XM station 68 (Spa) will be playing softly in the background via overhead speakers. If the patient had planned to listen to their own music during the procedure, this will be permitted and documented. Procedure consent and preprocedural preparation (see below) will take place. The overhead lights will then be turned off, and two battery powered lanterns will be lit to provide dim lighting. Stirrups will be avoided, if possible, during the preparation and procedure.

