## RANDOMIZATION

A permuted block randomization scheme will be used to assign weeks in a 1:1 ratio to intervention or control. The permuted blocks will prevent clinic staff from being able to predict which weeks will be Relaxing Environment Package or control. However, it will not be possible to blind subjects, staff, or investigators. Our statistician will be blinded. Randomization of weeks rather than patients was selected to minimize impact to clinic flow and help prevent protocol deviation among our busy clinic staff who often have back-to-back procedures. It will also allow assessment of procedure team burnout. Patients will only participate in the study once.

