## Secondary Outcome Measures

**Procedure pain:** Pain during the chemodenervation procedure will be assessed using a visual analog scale for pain (Figure 2). The VAS for pain is a validated scale that ranges from 0-100mm^15. 0mm is equivalent to “no pain” and is located on the left. 100mm is equivalent to “worst possible pain” and is located on the right. Subjects are asked to draw a vertical line on the scale that corresponds to their level of pain during the procedure. Baseline scores will be collected on the day of the procedure in the research office after obtaining consent. Patients will then be asked to circle the pain scores that corresponded to the pain experienced during the procedure. This will be collected by study staff after the procedure once the patient is dressed.

**Satisfaction with experience:** Patient satisfaction with their procedure experience will be assessed using a visual analog scale for patient satisfaction (Figure 3). The VAS for patient satisfaction is a validated scale ranging from 0-100mm^16. 0mm is equivalent to “no satisfaction” and 100mm is equivalent to “extreme satisfaction”. Subjects are asked to draw a vertical line that corresponds to their level of satisfaction with their procedure experience.

**Procedure team burnout:** Procedure team burnout will be assessed using a Burnout Battery visual analog scale for healthcare worker burnout (Figure 4). This tool was created to assess the working energy states of healthcare providers and is correlated with the Maslach Burnout Inventory which is a validated 22 question survey regarding workplace burnout. The RN(s) assigned to chemodenervation procedures as well as the physician performing the procedure will fill out the Burnout Battery VAS at the beginning and end of the clinic day. Providers are asked to circle the battery that represents their current energy level.

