## ANALYTICAL PLAN

Descriptive statistics will be used to summarize baseline characteristics of treatment and control groups. Means and standard deviations (or medians and interquartile ranges) will be used to summarize continuous variables such as age, and frequencies and percentages will be used to summarize categorical variables such as first-time vs. repeat patient. Regression analyses will be performed to test the hypotheses about treatment effects on primary and secondary outcomes. Planned regression models can flexibly address missing data and include covariate adjustment for important prognostic variables (such as first-time vs. repeat patient), as necessary. Exploratory subgroup analyses will be performed to characterize treatment effects within groups of interest, such as first-time or repeat patients.

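### The burnout analysis leaves open which variable is tested and names no staff or randomized-week term, although the arm is assigned by week.

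*Combined protocol and SAP*

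**What the plan says.** Burnout is the third of the Secondary Objectives: "Determine if the Relaxing Environment Package decreases procedure staff burnout based on a visual analog scale". The Hypothesis section repeats it as an expected reduction among exposed staff. Under Secondary Outcome Measures, "The RN(s) assigned to chemodenervation procedures as well as the physician performing the procedure will fill out the Burnout Battery VAS at the beginning" and again at the end of the clinic day. The scale has seven levels, from no bars to six.

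The arm is set by week: "On Monday of every week, an envelope will be opened to determine if it is a Relaxing Environment Package week or Control week". The Randomization section gives staff burnout as one benefit of this design: "It will also allow assessment of procedure team burnout". The study has a single center, and all physicians and procedure staff who assist with these procedures there are invited to take part.

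The Analytical Plan states: "Regression analyses will be performed to test the hypotheses about treatment effects on primary and secondary outcomes". It adds that the models can "include covariate adjustment for important prognostic variables (such as first-time vs. repeat patient), as necessary". The example covariate describes patients. The section says nothing specific to burnout, and no other section derives a burnout variable or describes a burnout model.

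**The concern.** Two scores a day can yield different endpoints: the end-of-day score, or the change over the day. For the primary outcome the protocol says that a change is analysed; for burnout it does not say.

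The person-days are also not independent. The same people score repeatedly, and everyone who works in a given week shares that week's arm and conditions. With one center, all such staff invited, and both arms present in every block of 4 or 6 weeks, the same people very likely score under both arms. That is an inference, since the documents give no roster.

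The Sample Size section recognises the weekly structure ("As the intervention is delivered at the week level"), but draws from it only that recruitment may run to the end of a week. If the burnout analysis ignored weeks, its standard error could be too small and produce a false claim of benefit. If it ignored staff who work evenly under both arms, the standard error could be too large and power would be lost.

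**Working it through.** **1. The plan's own figure.** Inputs from Sample Size: difference 12 mm, SD 18.8, 5% level (taken as two-sided), 80% power.

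n per arm = 2 × (1.96 + 0.84)² × 18.8² / 12² ≈ 38.5, so 39 per arm, or 78 in total. With a t-test, 40 per arm gives 80.5% power. The stated n=80 is therefore reproduced by a formula for independent patients, with no allowance for weeks. It concerns anxiety; no figure is given for burnout.

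**2. Inputs that must be assumed.** The documents give no number of staff, roster, number of weeks or burnout variances. Assumed: 3 physicians and 3 nurses, one of each per clinic day; 20 weeks in blocks of 4 or 6; 3 clinic days a week; residual SD 0.8 bars; staff SD 0.5 or 1.0; scores rounded to 0-6; no true effect. The full setting has week SD 0.3 and staff-by-week SD 0.4. The other settings halve these or set them to zero.

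**3. Hand checks of both directions.**

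- *Same pair all week, staff SD 0.5, full setting.* Total variance = 0.09 + 0.16 + 0.25 + 0.64 = 1.14. Two scores by one person in a week correlate (0.09 + 0.16 + 0.25)/1.14 = 0.44; scores by different people correlate 0.09/1.14 = 0.08. Each of the 6 weekly scores has 2 partners of the first kind and 3 of the second, so the mean correlation is (2 × 0.44 + 3 × 0.08)/5 ≈ 0.22. Design effect = 1 + 5 × 0.22 ≈ 2.1. Error = 2 × [1 − Φ(1.96/√2.1)] ≈ 18%. Simulation gives 16.3%; the hand formula ignores rounding and staff crossing arms.
- *Fixed weekdays, staff SD 0.5, no week variance.* Staff levels cancel between arms but stay in the pooled variance. True to assumed variance = 0.64/(0.64 + 0.25) = 0.72. Error = 2 × [1 − Φ(1.96/√0.72)] ≈ 2%. Simulation gives 2.9%.

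**4. Simulated error at nominal 5%, end-of-day person-days pooled as independent** (4,000 runs per cell; fixed-weekday row 2,000). Each cell shows staff SD 0.5, then 1.0.

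| Roster | Full week SDs | Half | Zero |
|---|---|---|---|
| Same pair all week | 16.3%, 16.4% | 11.1%, 15.0% | 8.6%, 13.4% |
| Pair changes daily | 11.2%, 8.6% | 6.7%, 4.7% | 4.2%, 4.0% |
| Pair keeps fixed weekday | 6.9%, 2.6% | 4.2%, 1.5% | 2.9%, 0.5% |

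Repeat simulations agree within simulation error, with the same-pair roster reaching about 18%. With 4 or 10 staff and 12 or 40 weeks (staff SD 1.0, full setting) the range was 8.1-19.2%.

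**5. Staff effects without a week term.** In the full setting: 14.7-16.0% with the same pair all week and 12.0-12.2% with daily changes. A staff term does not replace a week term.

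**6. Daily change, pooled.** 4.6-5.5% in the 12 cells of the first two rosters, because stable staff and week levels cancel. If within-day change itself varies by week (SD 0.3), about 7-9%.

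**7. Methods that respect the week.**

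- Comparison of week means (end-of-day score): about 4-6%.
- Staff fixed effects with week-clustered errors and bias-reduced (CR2) correction: 4.5-6.5%. A simple correction gives 4.9-7.9%, and up to 11.0% at the other sizes.
- Mixed model with random week and staff-by-week effects: about 2-6%.

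**The case against.** The strongest reply is that the plan states no wrong method. Regression with adjustment where needed covers a mixed model, and no section says that person-days will be pooled. That stands: the error rates above describe one way of filling the gap, not what the plan prescribes. A reader might infer that the plan will inflate false positives for burnout; the documents do not support that.

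Daily change is also a plausible intended endpoint, because scores are taken at both ends of the day and the primary outcome is a change. It would largely remove the problem. That also stands, but it is a reason to write the endpoint down, since two fair readings of the plan have different error rates.

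The direction depends on an unknown roster. With fixed weekdays the pooled test is mostly conservative. This too stands, so the upper figures must not be read as the expected size.

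The outcome itself is not undefined: instrument, raters and both time points are given. What is missing is the derived variable and the model. Finally, "Our statistician will be blinded" limits choice by arm, but settles neither of these.

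**Conclusion.** The gap is real and should be closed. A burnout test is planned with no derived variable and no staff or week term, and nothing elsewhere shows that the randomized week will be respected. Its size cannot be fixed from the documents. Under the assumptions shown, pooled end-of-day scores give about 9-18%, 4-11% or 0.5-7% by roster. The last range is mostly conservative and means lost power. Daily change gives near 5%, or about 7-9% if within-day change varies by week.

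A reader might also infer that the primary outcome is safe because this point concerns staff. The documents do not support that. Patients are assigned by week as well, and the Analytical Plan names no week term for them either. That belongs in a separate point.

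Burnout is a secondary outcome with no power claim, so this is a change the sponsor should make, not one on which the trial's main conclusion rests.

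**What to change.** In the Analytical Plan:

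- Name one burnout variable, either the end-of-day score or the daily change.
- Base inference on the randomized week. The simplest way is to compare week means between arms. The alternative is a person-day model with a staff effect and either random week and staff-by-week effects or week-clustered errors, with a small-sample correction (bias-reduced if clustered).
- If daily change is chosen, state that it measures the within-day effect only.
- State that start-of-day scores after the first clinic day of a week follow exposure to that week's arm. This matters whether those scores are subtracted or used as a covariate.

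The cost is a few sentences, a little more analysis work and possibly wider intervals. The mixed model is somewhat conservative (about 2-4%) if weeks do not differ. No new data are needed: staff are consented subjects, each subject has a study number, and the data forms carry that identifier.

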## ANALYTICAL PLAN

Descriptive statistics will be used to summarize baseline characteristics of treatment and control groups. Means and standard deviations (or medians and interquartile ranges) will be used to summarize continuous variables such as age, and frequencies and percentages will be used to summarize categorical variables such as first-time vs. repeat patient. Regression analyses will be performed to test the hypotheses about treatment effects on primary and secondary outcomes. Planned regression models can flexibly address missing data and include covariate adjustment for important prognostic variables (such as first-time vs. repeat patient), as necessary. Exploratory subgroup analyses will be performed to characterize treatment effects within groups of interest, such as first-time or repeat patients.

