### **Inclusion Criteria**

- Non-pregnant females
- Age 18 years and older
- English as a primary language
- Scheduled for office intra-detrusor chemodenervation for diagnosis of OAB/UU/UUI
- Baseline visual analog scale for anxiety  $\geq 12\text{mm}$

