### **Interventions and Interactions**

Patients scheduled for office intra-detrusor chemodenervation will be contacted by study staff via phone to introduce the study and gauge interest in participating. Interested and eligible patients will be asked to arrive thirty minutes before their scheduled procedure time to complete the consent process. Upon arrival, patients will be escorted to a research office where informed consent will be obtained. After obtaining informed consent, all participants will fill out a pre-procedure visual analog scale (VAS) for

anxiety (Figure 1) and a VAS for pain (Figure 2). If all inclusion criteria are met, including VAS-anxiety  $\geq 12$ mm on 100mm scale, participants will be enrolled and then escorted to the procedure room.

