## OUTCOME MEASURES

### Primary Outcome Measure:

The primary outcome is to compare the mean change in patients' anxiety level from when they arrive for their procedure to their anxiety level after at least 10 minutes of exposure to the relaxing or typical office environment (while the lidocaine anesthetic is given time to work in the bladder). The mean change in anxiety levels will be compared between the intervention and control groups. Anxiety will be assessed using a visual analog scale (VAS) (Figure 1). The VAS for anxiety is a validated scale that ranges from 0-100mm^14. 0mm is equivalent to "no anxiety" and is located on the left. 100mm is equivalent to "extremely anxious" and is located on the right. Subjects are asked to draw a vertical line on the scale that corresponds to their level of anxiety. The first VAS anxiety score (baseline) will be collected the day of the procedure in the research office after obtaining consent. The second VAS anxiety score (after exposure) will be collected just prior to starting the procedure after at least 10 minutes of exposure to the procedure room environment. The minimum clinically important difference for VAS anxiety is a change of 12mm on a 100mm scale.

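### Baseline VAS-anxiety, recorded for every enrolled patient, is not named as a covariate in the primary model; prespecify it

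*Combined protocol and SAP*

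**What the plan says.** The section on the primary outcome measure defines the endpoint as change in VAS-anxiety from arrival to after at least 10 minutes in the room: "The mean change in anxiety levels will be compared between the intervention and control groups". On the timing of baseline it states: "The first VAS anxiety score (baseline) will be collected the day of the procedure in the research office after obtaining consent".

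That score also decides entry. The Inclusion Criteria list "Baseline visual analog scale for anxiety" with a threshold of 12 mm. Under Interventions and Interactions, patients are scored first, and only if they qualify "participants will be enrolled and then escorted to the procedure room". Baseline is therefore measured before exposure and is complete by design.

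The Analytical Plan is one paragraph. It plans regression for the primary and secondary outcomes and says the models can "include covariate adjustment for important prognostic variables (such as first-time vs. repeat patient), as necessary". First-time or repeat status is the only covariate it gives as an example. No section writes out a primary model, names baseline VAS-anxiety as a covariate, or says when adjustment counts as necessary.

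**The concern.** Read together, the two sections point to an unadjusted comparison of change, with adjustment as an option. Unadjusted change fixes the coefficient of baseline at 1. Regression on baseline estimates that coefficient. In large samples the adjusted estimate is at least as precise, and it also removes the linear effect of a chance baseline difference between arms.

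Two things are at stake. The first is power: the stated sample size just reaches 80% before any allowance for randomising weeks, so there is little margin to give away. The second is prespecification: without a rule for necessity, the covariate set stays open until the data are in hand. The Randomization section says "Our statistician will be blinded". That limits a choice driven by the result, but it does not put the covariate in the plan.

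**Working it through.** **Inputs from the documents.** Sample Size: 80 patients, difference 12 mm, 80% power, "assuming a standard deviation of 18.8 and p-value 0.05". Randomization: weeks allocated 1:1.

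**Inputs assumed.** Correlation rho between baseline and follow-up scores 0.3 to 0.8; ratio k of follow-up SD to baseline SD, 1 or 1.25; intraclass correlation (ICC) of patients within week 0.05; 10, 20 or 40 weeks of equal size. The documents give none of these. They also do not say whether 18.8 is the SD of change or of a single score; it is taken as the SD of change unless stated. Tests are two-sided at 0.05. The 0-100 mm limits and the 12 mm entry cut are ignored.

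**1. The plan's own figure.** With 40 independent patients per arm, SE = 18.8 × √(2/40) = 4.20 mm. The noncentral t with 78 df gives power 80.5%. The stated n = 80 is therefore reproduced as an unadjusted two-sample comparison of independent patients.

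**2. Effect of adjustment, independent patients.**

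Adjusted variance / variance of change = k²(1 − rho²) / (1 + k² − 2·rho·k).

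For k = 1 this is (1 + rho)/2. Adjusted power uses 77 df; unadjusted power is 80.5% throughout.

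| k | rho | Variance ratio | Adjusted SD (mm) | Adjusted power |
|---|---|---|---|---|
| 1 | 0.3 | 0.65 | 15.16 | 93.8% |
| 1 | 0.5 | 0.75 | 16.28 | 90.2% |
| 1 | 0.7 | 0.85 | 17.33 | 86.4% |
| 1.25 | 0.3 | 0.784 | 16.65 | 88.9% |
| 1.25 | 0.5 | 0.893 | 17.76 | 84.7% |
| 1.25 | 0.7 | 0.981 | 18.62 | 81.2% |
| 1.25 | 0.8 | 1.000 | 18.80 | 80.5% |

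**3. Effect of adjustment, weeks randomised.** With W weeks and m = 80/W patients per week, and with the ICC component not reduced by baseline:

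Variance of the arm difference = (4/W) × [0.05 × 18.8² + ratio × 0.95 × 18.8²/m], df = W − 2.

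For example, with W = 20 and m = 4 the unadjusted variance (ratio 1) is 20.32, SE 4.51 mm. At rho 0.5 and k = 1 (ratio 0.75) it is 16.13, SE 4.02 mm.

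| Weeks | Unadjusted | Adjusted, k = 1, rho 0.3 / 0.5 / 0.7 | Adjusted, k = 1.25, rho 0.3 / 0.5 / 0.7 |
|---|---|---|---|
| 10 | 57.8% | 69.9 / 66.1 / 62.6% | 64.8 / 61.1 / 58.4% |
| 20 | 71.2% | 84.7 / 80.7 / 76.7% | 79.3 / 75.1 / 71.8% |
| 40 | 77.5% | 90.7 / 87.0 / 83.1% | 85.7 / 81.5 / 78.2% |

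The gain is about 5 to 13.5 points for k = 1 and about 0.6 to 8 points for k = 1.25. It is zero at k = 1.25 and rho 0.8. A simulation of the k = 1 case (20,000 trials per setting, unbounded normal scores, week-level t test) agreed with the formula within 1 point, with type I error of 4.8 to 5.4%.

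**4. If 18.8 is the SD of a single score** (k = 1, independent patients). The SD of change is 18.8 × √(2(1 − rho)) and the adjusted SD is 18.8 × √(1 − rho²). Power is 66.4% against 84.0% at rho 0.3, 80.5% against 90.2% at 0.5, and 95.3% against 97.7% at 0.7.

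**5. Chance imbalance** (k = 1, independent patients, 18.8 as SD of change). The baseline SD is 18.8/√(2(1 − rho)), which is 15.9, 18.8 and 24.3 mm at rho 0.3, 0.5 and 0.7. One standard error of the baseline difference between arms is that SD × √(2/40), or 3.6, 4.2 and 5.4 mm. A difference of that size shifts the unadjusted change by (1 − rho) times it: 2.5, 2.1 and 1.6 mm, against the 12 mm target.

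**6. Cost if baseline is useless.** With a variance ratio of 1, independent-patient power goes from 80.49% (78 df) to 80.48% (77 df).

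**The case against.** The plan already allows covariate adjustment, and its example is not a closed list, so a pre-exposure score on the outcome scale fits within its wording. Nothing says the primary model is unadjusted. This is right as far as it goes: the gap is an unnamed covariate and an option without a rule, not an invalid analysis. But permission to adjust does not fix the primary model.

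The size of the gain rests on inputs the documents do not give. That stands. It is about 0.6 to 8 points in the week design at an SD ratio of 1.25, larger if follow-up scores are less variable than baseline, and about 2 to 18 points if 18.8 is a single-score SD. The 12 mm entry cut narrows the baseline range and probably lowers the gain by an unknown amount. None of this reverses the direction.

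The handling of week is the larger analytic question. With 10 weeks, adjusted power is still only 62.6 to 69.9% in the equal-variance case. That also stands: baseline adjustment does not deal with clustering. Nor does it cure selective enrolment, which is possible because allocation is known before patients are consented and scored: "On Monday of every week, an envelope will be opened to determine if it is a Relaxing Environment Package week or Control week".

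**Conclusion.** The concern holds, as a matter of efficiency and prespecification. The stated sample size is not wrong on its own assumptions, and unadjusted change is unbiased under chance imbalance. With equal variances, 18.8 mm as the SD of change and correlations of 0.3 to 0.7, naming the covariate is worth roughly 6 to 13 points of power for independent patients. It is worth about 5 to 13.5 points in a week-randomised design with an ICC of 0.05. The gain can shrink to nothing under less favourable variance ratios. The absolute power figures for independent patients are too high for this design, and the documents cannot settle the exact gain. The change is worth making because the possible benefit is material and the cost is negligible.

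**What to change.** Keep the change endpoint as defined. Add one sentence to the Analytical Plan: the primary analysis regresses change in VAS-anxiety on arm and continuous baseline VAS-anxiety, and reports the adjusted mean difference with its 95% CI. Using the second VAS-anxiety score as the response instead gives the same arm estimate and standard error, provided baseline is in the model.

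This needs no extra data, visits or patients and adds one patient-level parameter. The method of accounting for week must be settled separately and has its own cost in degrees of freedom. The baseline term can be included whichever method is chosen.
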